H1: Participants who receive in-depth AM information are more likely to choose AM post-tool compared to participants in the control group.

Secondary Outcome 1: Post-tool acceptability of the different treatment options. Measured as categorical 5-point Likert scale from “Not at all comfortable” (1) to “Very comfortable” (5); analyzed as continuous variable. The following question is repeated four times, each time substituting OPTION X for one of the four treatment options:

- Q2.1: How comfortable would you be with **OPTION X** as your initial treatment for DCIS?

H2.1: Participants who receive in-depth AM information report higher AM acceptability compared to participants in the control group.

Secondary Outcome 2: Subjective perception of active monitoring riskiness. Measured as categorical 5-point Likert scale from “Not at all likely” (1) to “Very likely” (5); analyzed as continuous variable.

Q2.2: If you choose active monitoring as your treatment, how likely is it that your DCIS will progress to invasive cancer within 10 years after diagnosis?

- (1) Not at all likely
- (2)
- (3)
- (4)
- (5) Very likely

H2.2: Participants who receive in-depth AM information perceive AM to be subjectively less risky than participants in the control group.

Secondary Outcome 3: Post-tool mastectomy choice. Presented to participants as a categorical item: active monitoring, lumpectomy, lumpectomy with radiation, mastectomy. Recorded for analysis as binary: mastectomy vs non-mastectomy.

Q2.3: see Q1

H2.3: Participants who receive in-depth AM information are less likely to choose a mastectomy compared to participants in the control group.

Secondary Outcome 4: Change in self-perceived knowledge about DCIS. Measured pre- and post-tool as a categorical 5-point Likert scale from “I know very little about DCIS” (1) to “I know a lot about DCIS” (5); analyzed as continuous variable.

Q2.4: How much do you know about ductal carcinoma in situ, abbreviated as DCIS?

- (1) I know very little about DCIS
- (2)
- (3)
- (4)
- (5) I know a lot about DCIS

H2.4: In both groups, self-perceived knowledge about DCIS is higher post-tool compared to pre-tool.

H. Exploratory Aims

See next sections for details about covariates and additional scales used in the explanatory aims.

Exploratory Aim1: Descriptive analyses of the following scales:

- a) DCIS knowledge (11 questions), including AM knowledge (2 questions)
- b) Choice confidence (1 question)
- c) Information needs satisfaction

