To answer the primary research question, we will use a log-binomial regression model to test the effect of study arm on binary treatment choice (see primary outcome measure), controlling for age group to account for the stratified design:

$$(1) \quad Y_i = \beta_0 + \beta_1 X_i + \beta_2 a_i$$

where

Y_i = subject i 's response: $Y=1$ for AM, $Y=0$ for non-AM choice

X_i = subject i 's study arm: $X=0$ for control arm, $X=1$ for intervention arm

a_i = subject i 's age group: $a=0$ for age <65 years, $a=1$ for age ≥ 65 years

The main effect of interest (1) is represented by β_1 which quantifies the difference in AM uptake between the two arms and will be reported as $\exp(\beta_1)$ with 95% confidence interval [CI].

To follow the CONSORT statement and because the control arm prevalence is expected to be $>10\%$ we will report risk ratios as the relative measure, and absolute risks in both arms.

K.3. Secondary outcome analyses

Secondary Outcome 1. Linear regression model, as in (1), reported as β_1 (95% CI).

Secondary Outcome 2. Linear regression model, as in (1), reported as β_1 (95% CI).

Secondary Outcome 3. Same analysis as primary outcome analysis, reported as β_1 (95% CI).

Secondary Outcome 4. Linear regression model, controlling for age group, and with random intercepts to account for within-subject dependence.

Model:

$$(1) \quad Y_{ij} = \beta_0 + \beta_1 X_i + \beta_2 t_j + \beta_3 t_j X_i + \beta_4 a_i$$

where

Y_{ij} = subject i 's response at time t_j . (0=surgical; 1=AM)

t_j = time (0=pre-tool; 1=post-tool)

X_i = subject i 's study arm (0 = control; 1 = intervention)

a_i = subject i 's age group: $a=0$ for age <65 years, $a=1$ for age ≥ 65 years

If the models for secondary outcomes 1-4 do not meet the required assumptions for linear models, we will explore using median regression and/or dichotomizing the continuous variable (e.g., top quartile=high, remaining values=normal/low).

K.4. Exploratory aims analyses

Ad hoc statistical analyses will be performed for exploratory aims 1-4. For Exploratory Aim 5 (association of covariates and additional scales with choice), we will extend the model (1) to include covariates and additional scales as outlined sections I and J above. The additional model features will first be assessed for multicollinearity, with features removed if necessary. We will do model building to identify a final model, and present both unadjusted and adjusted parameter estimates for the final model (Table 3).

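### The fallback for the 5-point secondary outcomes (median regression and/or a top-quartile split) suits single 5-point items poorly and lets the method be chosen after the data are seen

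*SAP*

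**What the plan says.** SAP section G defines Secondary Outcomes 1 (acceptability), 2 (perceived riskiness of active monitoring) and 4 (self-perceived DCIS knowledge) as single 5-point items treated as continuous. For acceptability it reads "Measured as categorical 5-point Likert scale from “Not at all comfortable” (1) to “Very comfortable” (5); analyzed as continuous variable". Secondary Outcome 3, mastectomy choice, is "Recorded for analysis as binary: mastectomy vs non-mastectomy".

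Section K.3 then assigns the methods:

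- Outcome 1: "Secondary Outcome 1. Linear regression model, as in (1), reported as β_1 (95% CI").
- Outcome 2: "Secondary Outcome 2. Linear regression model, as in (1), reported as β_1 (95% CI").
- Outcome 3: "Secondary Outcome 3. Same analysis as primary outcome analysis", that is, the log-binomial model.
- Outcome 4: a linear model "with random intercepts to account for within-subject dependence".

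The closing sentence of K.3 sets the contingency. Its trigger is "If the models for secondary outcomes 1-4 do not meet the required assumptions for linear models" and its response is "we will explore using median regression and/or dichotomizing the continuous variable (e.g., top quartile=high, remaining values=normal/low".

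The SAP does not say which assumptions are checked or by what test and threshold. It does not say which fallback comes first, how responses tied at the quartile are coded, or whether the linear result is still reported. It gives no effect size, standard deviation or power for any 5-point outcome.

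**The concern.** A contingency rule is useful only if the alternative behaves better than the method it replaces. Here both named alternatives handle a five-value item worse than linear regression does. The median of such an item moves in whole steps, so median regression either sees nothing or sees a full point. A quartile rarely falls between two of five response values, so the size of the high group depends on how ties are coded.

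The open choice between the two methods, with no stated trigger, also means that the final tests of H2.1 (acceptability) and H2.2 (perceived risk) could be selected with results in view. For H2.4, a pre/post contrast, the sentence does not say how the random intercepts would be kept, or whether the quartile would be set once or separately at each time. Outcome 3 is listed although no linear model is planned for it.

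**Working it through.** **Inputs from the documents.** 101 completers per arm (SAP section E), significance level 0.05 (sidedness not stated; two-sided reproduces the SAP's table), 1:1 allocation stratified by age group, 5-point items, and a linear model with arm and age group.

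**Inputs assumed.** All response distributions and effect sizes for the 5-point items, because the documents give none.

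**Step 1. The plan's own power figure.** For 5% v 20% with pooled p = 0.125:

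- Null SE = √(2 × 0.125 × 0.875 / 101) = 0.0465
- Alternative SE = √((0.05 × 0.95 + 0.20 × 0.80) / 101) = 0.0453
- Power = Φ((0.15 − 1.96 × 0.0465) / 0.0453) = Φ(1.30) = 90.3%, against the stated 90%

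The other five scenarios give 80.6, 99.9, 98.2, 87.9 and 62.6%, against 80, 99, 98, 88 and 62%. The table reproduces, but it concerns the primary outcome only.

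**Step 2. Cost of an exact top-25% split on a continuous normal scale.** A standardised difference of 0.394 gives the linear analysis Φ(0.394 / √(2/101) − 1.96) = Φ(0.84) = 80% power. Cutting the pooled distribution at its top 25% gives 18.8% v 31.2% high. The formula of step 1 then gives 53% power, a loss of 27 points. About 192 per arm would be needed to recover 80%. Over starting powers of 50–95% the loss is 20–27 points.

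**Step 3. Why the quartile cannot be cut at 25% on five values.** With equal shares of 20%, the cumulative shares are 20, 40, 60, 80 and 100%, so the 75th percentile is the value 4. At or above it lie 40%; strictly above it lie 20%. With shares 5, 10, 20, 25 and 40%, the 75th percentile is 5: at or above it lie 40%, above it nobody. Across the simulations below, the supposed 25% group held on average 31–49% (≥ coding) or 0–20% (> coding).

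**Step 4. Simulation.** 1,000 trials per cell, 101 per arm, with a proportional-odds shift (log odds ratio about 0.7 to 0.8) chosen to give the linear model roughly 80% power. Median regression uses usual standard errors. Control-arm shares for values 1–5 are in the first column.

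| Control shares, % | Linear power | Split ≥ | Split > | Median regression power | Median regression type I error |
|---|---|---|---|---|---|
| 10/20/40/20/10 | 79.2 | 68.1 | 40.5 | 25.1 | 0 |
| 20/20/20/20/20 | 77.2 | 59.9 | 18.6 | 87.1 | 12 |
| 40/25/20/10/5 | 81.2 | 74.0 | 53.1 | 72.5 | 5 |
| 5/10/20/25/40 | 78.0 | 78.7 | 0 | 89.9 | 4 |
| 20/30/25/15/10 | 79.7 | 62.4 | 38.2 | 55.3 | 31–36 |
| 30/15/10/15/30 | 75.7 | 65.3 | 0 | 88.3 | 45–46 |

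- Loss with ≥ coding: 11.1, 17.3, 7.2, −0.7, 17.3 and 10.4 points, so about 0–17.
- Loss with > coding: 38.7, 58.6, 28.1, 78.0, 41.5 and 75.7 points, so 28–78.
- Type I error with no effect: linear regression about 3–6%; either split, fixed in advance, 0–6%.
- A separate set of runs, also at 101 per arm, gave 3–6% for linear regression and 0–48% for median regression. The split cut power of about 80% to 63–69% (≥) or 0–55% (>).

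Monte Carlo error is √(0.05 × 0.95 / 1000) = 0.7 points near 5%, and 1.3–1.6 points for mid-range power.

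**Step 5. Why median regression fails.** In the last row, with no effect, the fitted arm coefficient was exactly zero in 54% of trials. It was non-zero in 100 − 54 = 46%, and the test rejected in 45.4%. In the fifth row the figures are 100 − 64 = 36% and 36.1%; in the second, 100 − 88 = 12% and 12%. In these rows, almost any one-step difference in medians is declared significant. The higher power in some rows is partly this inflation.

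**Step 6. How often the fallback would start.** On residuals from 202 women, Shapiro-Wilk rejected normality in 99.8–100% of trials and Kolmogorov-Smirnov in 99–100%. Breusch-Pagan rejected in 4–7%, and a rule of absolute skewness above 1 was met in 0–2%.

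**Step 7. Outcome 4.** The two-arm simulation does not cover it. A separate check looked at which robust standard error suits paired ratings (202 women, no pre/post change, one symmetric distribution, least squares, 2,000 runs). HC3 errors, which ignore pairing, rejected in 2.5, 0.7 and 0.2% of trials at latent within-woman correlations of 0.3, 0.5 and 0.7. Errors clustered by participant rejected in about 5%.

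**The case against.** Several points on the other side stand.

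- A reader might infer that the fallback is bound to be used. The SAP names no check, and section G shows that the authors knowingly treat discrete items as continuous. Step 6 gives trigger rates from about 0% to 100% depending on a check that is not specified. The near-certain trigger holds only for a formal normality test.
- A reader might infer a fixed maximum loss of power. None can be derived: the documents give no effect size for these outcomes, and the loss depends on the assumed distribution and on tie coding.
- A reader might infer that the plan itself has a type I error near 50%. The worst rates need median regression with usual standard errors and an unfavourable distribution, or a deliberate choice of the better result. Taking the better of median regression and the ≥ split gave 3–47%; the better of the two codings gave 5–10%. The SAP does not say that the best result will be taken. It also names no standard error, and a percentile bootstrap of the difference in medians rejected in only 0–0.2% of null trials, which is very conservative.
- K.3 speaks of exploring, and the quartile is only an example. The Table 2 shell has means and SDs, and the Table 3 shell has β with a 95% CI. Both suggest that the linear result would still appear.
- Listing Outcome 3 is a drafting slip, since its own method is stated.

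These points limit the size of the problem but do not remove it. The methods that the SAP names are unsuitable whenever they are used, and nothing in it requires the linear result to stand as the main analysis.

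**Conclusion.** The concern holds in a limited form. The fallback would exchange an analysis that kept a type I error of about 3–6% for one of two worse ones. Median regression with usual standard errors ranged from about 0% to 48%. A top-quartile split is valid if fixed in advance, but lost roughly 0–17 points of power with ≥ coding and more with >. Leaving the choice and the trigger open allows selection after the data are seen. Non-normal residuals alone are no reason to leave the linear model at this sample size.

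These sizes rest on assumed response distributions and shifts. For Outcome 4 the objection rests on the wording and the paired design, not on a simulation of the fallback. Only secondary outcomes are affected; the primary analysis is not.

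**What to change.** Delete the fallback sentence in K.3 and state instead:

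- Outcomes 1 and 2 are analysed by the planned linear models with heteroscedasticity-robust (HC3) standard errors, whatever the residual distribution.
- Outcome 4 is analysed by the planned random-intercept model. If robust errors are used, they are clustered by participant; HC3 is not used there because it ignores the pairing.
- One ordinal sensitivity analysis is named: a proportional-odds model with the same terms, plus a participant random effect or clustering for Outcome 4.
- Outcome 3 keeps the log-binomial analysis and is not covered by any linear-model contingency.

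The cost is SAP wording and one extra model per outcome. No new data are needed.

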- d) Preparation for decision making
- e) Treatment choice reason

Exploratory Aim 2: Does knowledge about AM mediate AM acceptability?

Exploratory Aim 3: Is the score of the minimizer-maximizer scale associated with post-tool treatment choice?

Exploratory Aim 4: Are extreme scores of the minimizer-maximizer scale (1 or 6) associated with less accurate DCIS knowledge?

Exploratory Aim 5: What covariates and personality scales are associated with post-tool treatment choice and AM acceptability?

Exploratory Aim 6: Does subjective perception of AM riskiness mediate choice of AM?

I. Covariates

1) Age: Will be known before participation begins due to the recruitment method; will be used to ensure equal study arm assignment within the two stratification groups. For the analysis we will use self-reported age (years).

2) Race & Ethnicity: Asked as two separate questions

Are you Hispanic or Latina?

- Yes
- No

With which of the following groups do you most closely identify?

- White (1)
- Black or African American (2)
- American Indian or Alaska Native (3)
- Asian or Pacific Islander (4)
- Other (5)

3) SES: 4-level categorical variable

How would you describe your household's financial situation right now?

- After paying the bills, you still have enough money for special things you want
- You have enough money to pay the bills, but little spare money to buy extra or special things
- You have money to pay the bills, but only because you have cut back on things
- You are having difficulty paying the bills, no matter what you do

4) Education: 6-level categorical variable. May be recoded (e.g., college vs no college)

What is your highest level of education?

- Some high school
- High school
- Bachelor's degree
- Master's degree
- Professional degree (e.g., MD, JD)
- Doctorate degree (e.g., PhD)

5) Marital Status: 6-level categorical variable. May be recoded (e.g., married vs not married)

What is your current marital status?

- In Relationship
- Married
- Divorced
- Separated
- Single
- Other

6) Short Graph literacy. Single score derived from 4 items, each scored as correct or incorrect. Correct answers are summed for a total "graph literacy score" (0-4). See "Survey" document for details.

7) Current Health. Self-reported health status (visual analog scale, 0-100%), see "Survey" document for details.

J. Additional scales (See "Survey" documents for details about each scale)

- Choice confidence (Chambers et al., 2012) (post-tool)

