Finally, we will perform exploratory attrition analyses. First, we will compare the number of participants who expressed interest, consented, started the experiment, finished the experiment, and were included in final analysis. Second, if there are 20 or more participants who started the experiment but did not finish it, we will compare any completed baseline items

K.5. Missing Data

During data checks, we will determine the degree to which variables of interest are going unanswered. Depending on the type of variable and the amount of missingness across all subjects, as well as the balance across study arms, we will consider different imputation methods, or removal of the covariate from the models. For variables with a low degree of missing values (<=5%), we will use simple imputation methods, substituting in the median or modal response. For variables with a higher degree of missing values (>5%) we may perform multiple imputation with 25 imputations.

K.6. Subgroup Analysis

Stratification by age group (<65 vs. \geq 65 years) will occur during study arm assignment to ensure equal age group representation in each study arm. Further, we plan to analyze the effect of study arm on treatment choice separately within each of the two major age groups, while still including age in years as a continuous covariate. If there is a very marked difference in the stratified analysis, we could consider only including the stratified analysis (i.e. if the overall model is a poor indication of treatment effects because of the subgroup differences).

K.7 Sensitivity Analyses

Intent-to-treat vs. per Protocol analysis: Run both Table 1 and primary outcome model for the final sample with all exclusion criteria applied, as well as for the larger sample of all participants who were randomized and completed the post-survey. This comparison will only be necessary if >5% of those randomized, who completed the post-survey, were excluded due to not clicking through the guide and tool (new criteria).

Anticipated tables and figures

Table 1. Participant characteristics (demographic, pre-knowledge), overall and by treatment arm

Table 2. Primary and secondary outcomes at each time point, and change, by treatment arm

Table 3. Intervention effects on primary outcome

Figure 1: Proportion of treatment choice selections post-tool by study arm (*format TBD*)

Table 1. Patient characteristics, overall and by arm (demographics by age group included as a supplemental table)

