	Overall	Intervention	Control	p-value
Demographics				
Age (mean, SD)				
Age group				
<65				
≥ 65				
Sex (Female, N (%))				
Age (mean, SD)				
Race/Ethnicity				
African-American / Black				
American Indian or Alaska Native				
Asian or Pacific Islander				
Hispanic				
White				
Marital Status				
In a relationship				
Married				
Divorced				
Separated				
Single				
Other				
Education				
High school or less				
Some college				
College graduate				
Post-graduate degree				
Rural (N, %)				
Cancer History				
Maximizer Minimizer Scale (mean, SD)				
General pre-tool Knowledge (mean, SD)				
Breast Cancer				
DCIS				
Additional Scales (TBD)				

Table 2. Primary and secondary outcomes at each time point, by treatment arm

	Control	Intervention
Primary Outcome		
Treatment Choice (AM, N, %)		
Secondary Outcomes		
AM Acceptability (mean, SD)		
AM Perceived Risk (mean, SD)		
Mastectomy uptake (N, %)		
Change in self-perceived DCIS knowledge (post-pre, mean, SD)		

Table 3. Intervention Effects on primary and secondary outcomes

	Intervention Effect Overall		Intervention effect: <65 years		Intervention effect: ≥65 years	
Primary Outcome	RR (95%CI)	ARR (95% CI)	RR (95%CI)	ARR (95% CI)	RR (95%CI)	ARR (95% CI)
Choose AM at post-tool						
Risk ratio (95% CI)						
Absolute risk (95% CI)						
	Intervention Effect		Intervention effect: <65 years		Intervention effect: ≥65 years	
Secondary Outcomes	β (95% CI)	aβ (95% CI)	β (95% CI)	aβ (95% CI)	β (95% CI)	aβ (95% CI)
AM Acceptability						
AM Risk						

RR, relative risk; ARR, adjusted relative risk. Adjusted models include [covariate list] as covariates

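### SAP K.4 lets post-tool scales about the website, DCIS/AM knowledge or the choice into a model with study arm, and cites a Table 3 whose adjustment set is blank

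*SAP*

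**What the plan says.** Section H of the SAP words Exploratory Aim 5 as: "What covariates and personality scales are associated with post-tool treatment choice and AM acceptability". Section J lists the personality scales as one entry among many; it comprises risk attitude, pain tolerance, importance of appearance and cancer fear.

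K.4 restates the aim as "association of covariates and additional scales with choice". This is wider on scales, and it drops AM acceptability as an outcome. K.4 then says "we will extend the model (1) to include covariates and additional scales as outlined sections I and J above". Model (1), in K.2, has terms for study arm and age group. The screen is: "The additional model features will first be assessed for multicollinearity, with features removed if necessary". Model building follows, with no stated rule, and the SAP will "present both unadjusted and adjusted parameter estimates for the final model (Table 3".

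The table shell is titled "Table 3. Intervention Effects on primary and secondary outcomes". Every column is an intervention effect (RR and ARR, or β and aβ), overall and by age group, and no row is for a covariate. Its footnote reads "ARR, adjusted relative risk. Adjusted models include [covariate list] as covariates".

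Two other exploratory aims bear on this. Aim 1 puts DCIS knowledge, choice confidence, information needs satisfaction and preparation for decision making under descriptive analysis. Aim 2 asks whether AM knowledge mediates AM acceptability.

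**The concern.** Five scored scales in Section J are answered after the website has been used and concern the website, its content or the choice. Three carry a post-tool label in Section J: choice confidence, information needs satisfaction and preparation for decision making. The two knowledge scales carry no label, but in the survey in protocol Appendix 1 the knowledge items come after the website. All five also come after the treatment-choice question.

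The arms differ in AM content (SAP Section D), and some knowledge items ask about outcomes under AM, so arm may well change these scores. Choice confidence refers to the choice already made. If arm changes a scale that is also related to choice, conditioning on it removes part of the arm effect or distorts it. A multicollinearity check does not look at timing or causal position, so it would not remove such a scale.

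What is at stake is one set of numbers. An estimate that is not the total effect of arm could be printed under an intervention-effect heading, beside the unadjusted risk ratio, and be read as a better version of it.

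**Working it through.** **The SAP's own figure.** With 101 per arm, 5% against 20% and two-sided α = 0.05 (sidedness is not stated), the pooled formula gives z = (0.15·√101 − 1.96·√(2·0.125·0.875)) / √(0.05·0.95 + 0.20·0.80) = (1.5075 − 0.9167)/0.4555 = 1.297. Power is 90.3%, against the stated 90%. This point disputes no design figure.

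**Which scales each wording admits.**

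| Section J scale | K.4 | Aim 5 | Answered after the tool, about website, content or choice |
|---|---|---|---|
| Choice confidence | yes | no | yes |
| Information needs satisfaction | yes | no | yes |
| Preparation for decision making | yes | no | yes |
| Knowledge, de novo | yes | no | yes |
| Knowledge, decision quality instrument | yes | no | yes |
| Personality (4 scales) | yes | yes | no |
| Maximizer-minimizer | yes | no | no (about the person) |
| Health literacy | yes | no | no |
| Breast cancer knowledge, pre-tool | yes | no | no |

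**Candidate coefficients under K.4, without the intercept.**
- Arm: 1.
- Section I: age 1, Hispanic 1, race 4, finances 3, education 5, marital status 5, graph literacy 1, health 1 = 21.
- Section J: information needs 4 (items analysed separately) plus 11 other scorable scales at 1 each = 15.
- Total: 1 + 21 + 15 = 37, or 38 if age group stays beside age in years. Aim 5's wording gives 1 + 21 + 4 = 26.

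This is a maximum, before removal for multicollinearity, model building and the recoding that Section I allows.

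**Expected AM choices** = 101 × (P1 + P2), for the six scenarios in SAP Section E.

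| Scenario | P1, P2 | AM choices | per coefficient (÷ 37) |
|---|---|---|---|
| 1 | 5%, 20% | 25.25 | 0.68 |
| 2 | 10%, 25% | 35.35 | 0.96 |
| 3 | 10%, 40% | 50.50 | 1.36 |
| 4 | 15%, 40% | 55.55 | 1.50 |
| 5 | 20%, 40% | 60.60 | 1.64 |
| 6 | 25%, 40% | 65.65 | 1.77 |

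There are fewer than two AM choices per candidate coefficient throughout, so the unstated selection rule has much influence on the adjusted estimate for choice. The count does not apply to AM acceptability, which is a linear model on about 202 women.

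**Illustration of the mechanism. All inputs are assumed; the documents give none.** Take one post-tool scale M = d·arm + N(0,1). Choice is logistic in arm and M, with log-odds b per SD, and calibrated so that the marginal risks match the scenario. Compute the large-sample Poisson log-link risk ratio for arm adjusted for M (60-node Gauss-Hermite quadrature), with |b| from 0.2 to 0.8.

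| d (SD) | RR 4.0, b > 0 | RR 4.0, b < 0 | RR 2.5, b > 0 | RR 2.5, b < 0 |
|---|---|---|---|---|
| 0 | 4.00 | 4.00 | 2.50 | 2.50 |
| 0.1 | 3.76–3.93 | 4.07–4.25 | 2.36–2.46 | 2.54–2.65 |
| 0.25 | 3.43–3.84 | 4.17–4.66 | 2.16–2.40 | 2.60–2.89 |
| 0.5 | 2.95–3.68 | 4.34–5.43 | 1.87–2.31 | 2.70–3.34 |

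For a scale that follows the choice, such as choice confidence, a simulation of 400,000 women with the scale shifted 0.5 SD by arm and ±0.5 SD by choice gave 3.18 and 4.76 (age-adjusted value 4.02). With an arm shift of 0.5 SD and no relation to choice given arm, the ratio stayed at 4.0.

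For AM acceptability the change in the arm coefficient is shift × slope. With 0.1–0.5 SD and 0.1–0.5 points per SD, that is 0.01 to 0.25 points on the 1–5 scale.

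**The case against.** The strongest reply is that the SAP never intended this. Aim 1 sends the same five scales to descriptive analysis, and Section H introduces Sections I and J together as the material for the exploratory aims, so K.4's phrase may be shorthand. That stands as evidence of intent. It does not remove the conflict, because an analyst following K.4 as written may enter all of Section J.

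Second, Table 3 fits K.4 poorly. It has age-group columns that K.4 does not mention, an AM risk row outside Aim 5, and no covariate rows although K.4 promises parameter estimates. The citation may be a wrong table number. ARR could also mean age-adjusted: K.2 adjusts for age group, and K.6 plans within-stratum analyses "while still including age in years as a continuous covariate". This also stands. That K.4's model fills the ARR is an inference from its citation. For the AM acceptability aβ it is a further inference, from Aim 5's outcomes. For the AM risk aβ nothing supports it.

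Third, a reader might infer that the model cannot be fitted because candidates outnumber events. That is so only in scenarios 1 and 2. Scenarios 3 to 6 give 50.5 to about 66 AM choices, and K.2 itself expects control prevalence above 10%.

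Fourth, association models may legitimately contain post-tool variables. They may; the difficulty is only in labelling the arm coefficient from such a model an intervention effect.

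**Conclusion.** The point holds as a conflict of scope, together with an undefined adjusted effect. K.4 is wider than Aim 5, its only stated screen does not exclude measures that arm may change, and it cites a table of intervention effects whose adjustment set is blank.

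A reader might go further and conclude that the primary result is biased, or that the SAP plans to adjust it for mediators. The documents do not support that. K.2 and the K.3 arm comparisons adjust for age group only, the five scales are candidates rather than fixed terms, and Aim 5 is exploratory. Nor are the illustrative ratios a forecast. They show that a risk ratio of 4.0 could become anything from 2.95 to 5.43 under assumed shifts up to 0.5 SD and log-odds up to 0.8 per SD, and would not move if the scale did not differ by arm. The true size and direction are unknown.

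Severity is low. The exposure is confined to the ARR for AM choice and, by inference, the aβ for AM acceptability.

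**What to change.** 1. Reconcile K.4 with Aims 1 and 5 on which scales may enter, saying explicitly what happens to the maximizer-minimizer, health literacy and pre-tool breast cancer knowledge scales, which Aim 5's wording also leaves out. Bar scales measured after the tool that concern the website, DCIS or AM knowledge, or the choice from any model whose arm coefficient is reported as an intervention effect.
2. Report the Aim 5 association model in its own table, with its arm coefficient not labelled an intervention effect.
3. Replace the placeholder under Table 3 with a statement that ARR and aβ adjust only for named, prespecified variables that the tool cannot change, for example age and pre-tool knowledge, with no data-driven selection.

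The cost is SAP wording and one extra table. Sample size, data collection and the K.2 and K.3 analyses do not change.

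### The adjusted treatment-choice model needs an estimator other than log-binomial: with several scales among 202 women, its maximum often lies at a fitted probability of 1

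*SAP*

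**What the plan says.** SAP K.2 sets the primary analysis: "we will use a log-binomial regression model to test the effect of study arm on binary treatment choice", with age group as the only other covariate. Equation (1) is printed without a link function. The text and the reporting of an exponentiated coefficient show that a log link is meant.

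K.4, for Exploratory Aim 5, says "we will extend the model (1) to include covariates and additional scales as outlined sections I and J above". Those sections list age in years, graph literacy (0-4), self-rated health (0-100), the maximizer-minimizer item and scales for risk attitude, pain, appearance and cancer worry, besides categorical demographics. On reducing the set, K.4 says "The additional model features will first be assessed for multicollinearity, with features removed if necessary", followed by model building that is not described. The results go into Table 3.

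Table 3 has crude and adjusted risk-ratio columns, overall and for each age group. Its footnote reads "ARR, adjusted relative risk. Adjusted models include [covariate list] as covariates", so the list is still open.

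K.6 analyses the arm effect "separately within each of the two major age groups, while still including age in years as a continuous covariate".

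The only model fallback is in K.3. It applies where the secondary-outcome models, in the SAP's words, "do not meet the required assumptions for linear models, we will explore using median regression and/or dichotomizing the continuous variable". Nothing is said about a log-binomial model that does not converge, ends on the boundary or meets an empty cell.

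**The concern.** In a log-binomial model the linear predictor is the log of a probability, so it must be at or below zero for every participant. Two binary covariates rarely put this under strain. Continuous scales do: the fitted slope that suits most women can push those with extreme scores above a probability of 1. The constrained maximum then lies on the limit, the score equations are not solved there, and information-based standard errors do not apply. Many programs simply report non-convergence.

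At stake are the adjusted relative risks in Table 3 and the final model for Exploratory Aim 5. With no rule in the SAP, the analyst would have to choose after seeing the data whether to drop covariates, change starting values or change method. Within age strata there is a separate question: whether the control group contains any women who choose active monitoring. If not, the ratio has no finite value.

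**Working it through.** **1. Planning figures (SAP section E).** Two-sided alpha 0.05, 101 per arm, 5% against 20%, pooled proportion 0.125.
- Standard error under the null: √(2 × 0.125 × 0.875 / 101) = 0.0465.
- Under the alternative: √((0.05 × 0.95 + 0.20 × 0.80) / 101) = 0.0453.
- Power = Φ((0.15 − 1.96 × 0.0465) / 0.0453) = Φ(1.30) = 90.3%; stated 90%.
- The other five scenarios give 80.6, 99.9, 98.2, 87.9 and 62.6%, against 80, 99, 98, 88 and 62% stated.

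The planning table is sound, so its rates serve as inputs below.

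**2. Events and candidate terms.** At 5%/20%, expected choosers of active monitoring are 101 × 0.05 + 101 × 0.20 = 25.3. By my count sections I and J would add about 28-36 terms if everything entered; the lower figure has education and marital status recoded to two levels.

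**3. Adjusted model, full sample.** Assumptions not in the SAP: five-point scales, two of them predictive at a log odds ratio of 0.4 per SD and the rest null, and choices generated from a logistic model. The log-binomial likelihood was maximised under the constraint. The table gives the share of data sets with no interior maximum, for four of the SAP's six uptake pairs (150 runs per cell; Monte Carlo standard error at most √(0.25/150) = 4.1 points).

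| Control / intervention | 2 scales | 6 scales |
|---|---|---|
| 5% / 20% | 8% | 33% |
| 10% / 25% | 11% | 35% |
| 10% / 40% | 29% | 71% |
| 25% / 40% | 25% | 54% |

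- A 400-run repeat at 5%/20% gave 6.5% and 34%.
- A second simulation with the same effect size gave 1-15% with 2 scales and 27-64% with 6. The combined range is roughly 1-30% and 27-71%.
- The effect size matters. At 25%/40% with 6 scales, the share was 11% with no covariate effects, 57.5% at 0.4 per SD and 94% at 0.7 per SD.
- An unguarded fitting routine (no step control) failed in 40-91% of these data sets with 2 scales and 72-99% with 6. That is an upper bound on software failure.
- The primary model, arm plus age group, had no boundary solution in any scenario.

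**4. Modified Poisson on the same data.** It returned an estimate in 99-100% of runs, and 95% intervals covered in about 95-99%. Some fitted values exceeded 1 in 5-61% of runs.

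**5. Subgroup model of K.6 (arm plus age in years).** No interior maximum in 0-5% of runs if age has no effect, and up to 11% with an age effect and only 20 per arm.

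**6. Empty control cell.** With m controls in a stratum and control uptake p, P(no choosers) = (1 − p)^m. The SAP gives no age split.

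| m | p = 5% (section E) | p = 10% (K.2 expects more) |
|---|---|---|
| 20 | 36% | 12% |
| 30 | 21% | 4% |
| 50 | 0.95^50 = 7.7% | 0.90^50 = 0.5% |

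For strata of 50 and 51 controls, the chance of at least one empty cell is 1 − (1 − 0.95^50)(1 − 0.95^51) = 14% at 5%, and about 1% at 10%.

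In simulated strata of 30 per arm at 5%/20%, 19% of runs had an empty control cell. Modified Poisson gave no finite ratio in any of them.

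**The case against.** **The subgroup analysis.** A reader might infer that the K.6 ratios will often fail too. They will not, on the model as written: arm plus age in years usually fits. The 7.7% and 14% apply only at 5% control uptake with an assumed even split. K.2 expects control uptake above 10%, and five of the six planning scenarios use 10-25%. An empty cell is also no fault of the log-binomial model, since every unpenalised ratio estimator shares it. The SAP already promises absolute risks by arm, so the result would not vanish. All of this stands. What remains is that no rule covers an undefined ratio, while K.6 allows the stratified analysis to be the only one reported if the strata differ markedly.

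**Size of the final model.** The retained set is unknown and may be small. That stands, and it is why the result for 2 scales is given beside that for 6. The simulated effects are assumptions.

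**Adjusted ratios by stratum.** Table 3 leaves the list blank, and the only stratum covariate K.6 names is age in years. If scales were added there (30-50 per arm, control uptake 10% or more), the boundary share would be 20-47% with 2 and 62-90% with 6. The SAP does not say that they will be.

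**The replacement.** Modified Poisson does not make a large model with about 25 events trustworthy. That also stands: it cures the fitting problem, not overfitting or undescribed model building.

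**Consequence.** Aim 5 is exploratory. This limits the weight of the point but does not remove it, because the adjusted ratios share a table with the primary result.

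**Conclusion.** The point holds for the K.4 adjusted model of treatment choice and the adjusted risk-ratio columns of Table 3. The stated method would often have no valid standard errors there: roughly 1-30% of data sets with 2 scales and 27-71% with 6, at an assumed log odds ratio of 0.4 per SD for two scales. These are ranges under assumptions, not predictions; weaker effects lower them and stronger effects raise them. The linear models for acceptability are not concerned.

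Two stronger readings are not supported. The primary analysis is not in doubt, since the two-covariate model showed no boundary solutions. Nor are adjusted and subgroup ratios unreliable as a class: a boundary maximum is still a constrained maximum likelihood estimate whose standard errors are the problem, and the K.6 model usually fits. That covariate selection would in practice follow convergence is a plausible risk, but it was not simulated.

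This is a minor improvement to the SAP.

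**What to change.** - **K.2:** leave the log-binomial primary model unchanged.
- **K.4 and the adjusted risk-ratio columns of Table 3:** name modified Poisson regression with robust standard errors as the method. Logistic regression with marginal standardisation is an acceptable alternative that keeps fitted probabilities within 0 and 1. Either keeps the risk-ratio scale. Fill in the covariate-list placeholder at the same time.
- **K.6 and the age-group columns of Table 3:** beside the ratio, report the risk difference with a score-type interval, which exists even when a cell is empty. State that a ratio with no choosers in the control stratum is shown as not estimable.

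The cost is SAP wording. The statistical price is slightly less efficient standard errors than a log-binomial fit that does converge. No data collection, sample size or primary result changes.
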